9.8 Study size

This study aims to recruit sufficient patients to record 30 episodes per treatment per country. Given this, the number of patients recruited will range from 15 to 30 per treatment per country. To evaluate the value of the sample estimates of the population that this sample size will allow for, it will be assumed pessimistically that each patient will have one measurement; the estimates once the study is carried out will therefore have higher precision than calculated below.

The anticipated length of time for pre and post-administration activities and infusion for each treatment utilised estimates from the research of Guest et al.¹⁷ alongside clinical opinion sourced from sites in the countries of study; it was estimated that pre-administration processes would always take between 10-30 minutes, post-administration processes would take between 15-30 minutes, infusion of agalsidase alfa takes between 40 to 60 minutes and infusion of agalsidase beta would take between 90 to 180 minutes. To anticipate the precision of estimates given the sample size above, it was estimated that these times would follow a normal distribution within these ranges (as a result, the mean could be estimated by taking the middle value of the range and the standard deviation roughly approximated accordingly).

It is important to account for the fact that Fabry disease is rare and that the sample collected will represent a large proportion of the total population with disease. For instance, in the US, it was estimated that there were only approximately 7700 patients in total out of a population of about 323 million in 2016, which suggests that only 0.0024% have the disease. The estimated number of Fabry disease patients in other countries can be calculated from the prevalence of the disease in the US, by multiplying the expected proportion of the population with the disease (assuming that the prevalence is similar in the US to other countries) with the estimated total population (Brazil, Japan, Taiwan and Turkey therefore could have an estimated patient population of about 5015, 3033, 573 and 1934 patients respectively based on estimates of total population of 210 million, 127 million, 24 million and 81 million patients respectively²⁴). Accounting for this, the estimated precision of estimates of time at different sample sizes for the largest and smallest countries in the study by population can be seen in the table below.

Table 5. Sample size estimations

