Cohort	Activity / Estimate	95% confidence interval at different sample sizes			
		15 patients	20 patients	25 patients	30 patients
Brazil	Pre-Admin activity Mean: 20 minutes	17m 14 - 22m 46	17m 40 - 22m 20	17m 56 - 22m 04	18m 08 - 21m 52
	Post-Admin activity Mean: 22 mins 30	20m 26 – 24m 34	20m 45 – 24m 15	20m 57 – 24m 03	21m 06 – 23m 53
	ERT Alfa Mean: 50 minutes	47m 14 – 52m 46	47m 40 – 52m 20	47m 56 – 52m 04	48m 08 – 51m 52
	ERT Beta Mean: 135 minutes	122m 33 – 147m 27	124m 29 – 145m 31	125m 44 – 144m 16	126m 37 – 143m 23
	Overall Alfa Mean: 92 mins 30	84m 54 – 100m 06	86m 05 – 98m 55	86m 50 – 98m 10	87m 23 – 97m 37
	Overall Beta Mean: 177 mins 30	160m 13 – 194m 47	162m 54 – 192m 06	164m 38 – 190m 22	165m 52 – 189m 08
Taiwan	Pre-Admin activity	17m 16 – 22m 44	17m 42 - 22m 18	17m 59 - 22m 01	18m 08 - 21m 52

	Mean: 20 minutes				
	Post-Admin activity Mean: 22 mins 30	20m 27 – 24m 33	20m 46 – 24m 14	20m 59 – 24m 01	21m 06 – 23m 54
	ERT Alfa Mean: 50 minutes	47m 16 – 52m 44	47m 42 – 52m 18	47m 59 – 52m 01	48m 08 – 51m 52
	ERT Beta Mean: 135 minutes	122m 42 – 147m 18	124m 39 – 145m 21	125m 55 – 144m 05	126m 37 – 143m 23
	Overall Alfa Mean: 92 mins 30	84m 59 – 100m 01	86m 10 – 98m 50	86m 57 – 98m 03	87m 23 – 97m 37
	Overall Beta Mean: 177 mins 30	160m 24 – 194m 36	163m 07 – 191m 53	164m 52 – 190m 08	165m 52 – 189m 08

The higher the number of patients available to sample from the more precise the estimates of time taken for each activity will be, yet even at a worse-case scenario, 95% confidence intervals should be sufficient to describe the burden associated with ERT administration. Estimates taken from countries where the sample size represents a higher proportion of the total population with the disease, such as Taiwan will also be slightly more precise.

Therefore, the target sample size for the time and motion evaluation undertaken as part of this study is 240 ERT episodes, including 60 ERT episodes (30 for agalsidase alfa and 30 for

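### Protocol Table 5: Taiwan's 30-patient intervals were calculated with Brazil's population size, and the floor of 15 patients in section 9.8 ignores the three-episode exception

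*Protocol*

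**What the plan says.** Protocol section 9.8 aims for 30 episodes per treatment per country and concludes that "the number of patients recruited will range from 15 to 30 per treatment per country". For Table 5, "it will be assumed pessimistically that each patient will have one measurement", and from this the section infers that "the estimates once the study is carried out will therefore have higher precision than calculated below". The activity times are given as ranges, and "the mean could be estimated by taking the middle value of the range and the standard deviation roughly approximated accordingly". Patient populations are put at about 5015 for Brazil and 573 for Taiwan, the largest and smallest of the four countries.

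Table 5 then prints 95% confidence intervals for six activities at 15, 20, 25 and 30 patients in each of these two countries. For Overall Beta at 25 patients, Brazil has "164m 38 – 190m 22" and Taiwan "164m 52 – 190m 08". At 30 patients both have "165m 52 – 189m 08". The text below the table says precision is adequate even in the worst case, and that estimates from countries "such as Taiwan will also be slightly more precise".

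Later in section 9.8, three episodes per patient are allowed in exceptional cases where few patients are available, with two kept wherever possible. At least 30 patients per country are still expected. SAP sections 2.1 and 2.4 repeat the episode target and the exception, but give no precision figures.

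**The concern.** There are two separate points.

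1. The finite population correction shrinks Taiwan's interval more as the sample grows, so Taiwan's advantage over Brazil should be largest at 30 patients. In the table it disappears there. Five of the six rows are identical for the two countries, and in the sixth (post-administration) Taiwan is one second wider. That column contradicts both the rest of the table and the sentence about Taiwan.

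2. Thirty episodes from 15 patients is two episodes each. If some patients give three, fewer than 15 patients can supply the 30 episodes. The lowest column of Table 5 is then not the lowest patient number the design permits, and the assurance of higher precision may fail in the situation the exception was written for.

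Table 5 is the only precision justification in either document. The study is descriptive, with no test, power or target width, so what is at stake is the accuracy of that justification.

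**Working it through.** **Inputs.** From section 9.8: pre-administration 10–30 min, post-administration 15–30, alfa infusion 40–60, beta infusion 90–180; N = 5015 (Brazil) and 573 (Taiwan); one measurement per patient. The SD rule is not stated. I infer SD = range/4, because it reproduces the table: 5, 3.75, 5 and 22.5 min. The Overall rows apply the same rule to the summed ranges: (120 − 65)/4 = 13.75 for alfa and (240 − 115)/4 = 31.25 for beta.

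**Formula.** Half-width = t(0.975, n−1) × SD/√n × √((N−n)/(N−1)).

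**Reproducing the table.** Brazil, Overall Beta, n = 15: 2.1448 × 31.25/√15 × 0.9986 = 17.28 min, so 160m13–194m47 as printed. In all, 41 of 48 cells match to the second, including all 18 Taiwan cells at 15, 20 and 25 patients. Using z instead of t misses by up to 89 seconds. The seven mismatches are the six Taiwan 30-patient cells and one Brazil limit (post-administration, 30 patients, upper: printed 23m53, recalculated 23m54).

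**Taiwan, 30 patients, Overall Beta.**
- N = 573: 2.0452 × 31.25/√30 × 0.9743 = 11.369 min, giving 166m08–188m52.
- N = 5015: 2.0452 × 31.25/√30 × 0.9971 = 11.635 min, giving 165m52–189m08, the printed value.
- No correction: 11.669 min, giving 165m50–189m10. Omitting the correction is therefore not the explanation.

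| Taiwan, n = 30 | Printed (fits N = 5015) | With N = 573 | Excess per limit (s) |
|---|---|---|---|
| Pre-admin | 18m08–21m52 | 18m11–21m49 | 2.9 |
| Post-admin | 21m06–23m54 | 21m08–23m52 | 2.1 |
| ERT alfa | 48m08–51m52 | 48m11–51m49 | 2.9 |
| ERT beta | 126m37–143m23 | 126m49–143m11 | 11.9 |
| Overall Alfa | 87m23–97m37 | 87m30–97m30 | 6.9 |
| Overall Beta | 165m52–189m08 | 166m08–188m52 | 15.8 |

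Taiwan's expected gain per limit over Brazil for Overall Beta at 15/20/25/30 patients is 11.3/13.0/14.6/16.0 s. The printed gain is 11/13/14/0 s.

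**Patient floor.** At two episodes each, 30/2 = 15. At three each, 30/3 = 10. Two patients with three episodes are enough to go below 15: 2×3 + 12×2 = 30 episodes from 14 patients.

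**Precision at 10 patients, one measurement each.** Brazil Overall Beta: 2.2622 × 31.25/√10 × 0.9991 = 22.33 min (±22m20), against ±17m17 at 15. Overall Alfa is ±9m50, against ±7m36. For Taiwan the figures are ±22m11 and ±9m46. The ratio to the 15-patient half-width is 1.292 for Brazil and 1.298 for Taiwan.

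**Ten patients with three episodes each.** This needs the within-patient intraclass correlation (ICC), which the documents do not give, so I show the full range. Half-width = t(0.975, 9) × SD × √((1 + 2·ICC)/30) × finite population correction. Brazil Overall Beta, against the printed 15-patient ±17m17:

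| ICC | 0 | 0.25 | 0.5 | 0.75 | 1 |
|---|---|---|---|---|---|
| Half-width | ±12m54 | ±15m48 | ±18m14 | ±20m23 | ±22m20 |

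The interval is wider than the 15-patient column once the ICC exceeds 0.398 (Brazil) or 0.391 (Taiwan). For the same 10 patients, three episodes rather than one multiply the half-width by √((1 + 2·ICC)/3), which lies between 0.58 and 1.00. Repeats therefore never widen the interval at a fixed number of patients.

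**The case against.** The first error has no practical consequence. At most 16 seconds on a half-width of about 11.5 minutes is some 2.3%, and it is conservative. The SD is described as rough, and N = 573 is a US prevalence carried over to Taiwan. Nothing in the SAP uses the table. The sentence about Taiwan is right as a general statement; it is the column that is wrong. All of this stands and limits the point to a correction.

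On the floor, the exception is disclosed in the same section. Ten patients would need every patient to give three episodes, although three is meant to be exceptional. Ten in both treatments makes 20 per country, below the 30 or more expected. Whether precision is actually worse than in the 15-patient column depends on an unknown ICC, and ±22m20 is the extreme at ICC = 1. It is fair to call 10 the extreme. But the expectation of 30 is per country and does not guarantee 15 per treatment, and two patients with three episodes already break the stated floor. The unconditional range and the worst-case claim are therefore not correct as written.

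One could also argue that a single qualifying clause is enough and a 10-patient column is more than is needed. The clause corrects the statement. The column supplies the precision for the case the exception allows, and the figures are ready to use.

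**Conclusion.** Both points hold and both are minor. Taiwan's 30-patient column was calculated with Brazil's N. Its limits are 2 to 16 seconds too wide, and it shows none of the gain claimed for Taiwan. This rests on the inferred range/4 rule, which the match of 41 of 48 cells supports strongly. The range of 15 to 30 patients is true only at no more than two episodes per patient; under the exception the floor is 10. At 10 patients the table's own method gives half-widths 1.29 to 1.30 times those at 15. With three episodes each, the interval exceeds the 15-patient column only if the ICC is above about 0.40, which is an assumption the documents cannot settle. The higher-precision statement is sound when the number of patients is held fixed, and not otherwise. The 240-episode target and the conclusion that precision is sufficient do not change, since no target width is set.

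**What to change.** In Protocol section 9.8:

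1. Replace the six Taiwan 30-patient cells with the N = 573 values in the table above, and change Brazil's post-administration 30-patient upper limit from 23m53 to 23m54.
2. State that 15 to 30 patients per treatment per country assumes no more than two episodes per patient, and that the floor is 10 if every patient gives three.
3. Add a 10-patient column:

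| Activity | Brazil | Taiwan |
|---|---|---|
| Pre-admin | 16m26–23m34 | 16m27–23m33 |
| Post-admin | 19m49–25m11 | 19m50–25m10 |
| ERT alfa | 46m26–53m34 | 46m27–53m33 |
| ERT beta | 118m55–151m05 | 119m02–150m58 |
| Overall Alfa | 82m40–102m20 | 82m44–102m16 |
| Overall Beta | 155m10–199m50 | 155m19–199m41 |

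4. Reword the higher-precision sentence so that it claims at least the tabulated precision for the same number of patients.

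SAP sections 2.1 and 2.4 need no change, because they already tie the 30 patients per country to two episodes each. Enrolment, episodes and analysis are unaffected. The cost is seven cells, one column and a few sentences, plus the ethics committee notification that Protocol section 10.2 requires for any amendment, so this can wait for the next one. The stated worst case becomes somewhat wider.

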9.9 Data management

9.9.1 Data collection

Patient demographic data will be collected using an anonymised-coded standardised eCRF designed specifically for the study. Patients will be identified in all study records by a unique study code to link multiple study records for each participant (if applicable) and preserve patient confidentiality. Data will be collected by members of the care team at each centre or external researchers (to be confirmed in each country prior to study commencement) using an electronic data capture (EDC) system through eCRFs.

For the prospective time and motion component of the study, trained external observers who are independent of the care process will attend the hospital or treatment centre and observe consenting patients' episodes of care. Alternatively, episodes of care may be observed by trained members of the patients' care team at each site, who are not performing the tasks that are being observed. Data will be collected about the procedures involved in the preparation and administration of ERT with agalsidase alfa or agalsidase beta, the job roles of HCPs involved and the time taken to complete the activities (start and stop time for each activity); this will be measured from the start of the first activity related to ERT preparation / administration (e.g. start of the pre-infusion clinical assessment) until completion of the last activity related to ERT preparation / administration (e.g. completion of the post-infusion documentation). The time taken to prepare and dispense the relevant medication will also be

collected by observation of pharmacy or nursing staff (as appropriate). Data for the time and motion component of the study will be collected using an anonymised-coded standardised paper-based CRF designed specifically for the study. The anonymised-coded data will then be transcribed into the eCRF by an appropriate member of staff.

Data management for eCRFs will be carried out using MACRO™, a data management system which has a secure web-based data entry interface and is fully validated and compliant with Food and Drug Administration (FDA) Information Governance standard 21 Code of Federal Regulations (CFR) Part 11. The MACRO™ system has restricted access, role-based permissions for data entry management and analysis and maintains an audit trail of all changes to data and activity in the system in line with 21 CFR Part 11. Members of the whole care team and external researchers will be trained in data entry into the eCRFs by study management staff from Open Health. Entry to MACRO™ will be restricted (by password protection) to only those members of staff directly involved with the study.

Consenting patients and caregivers will be given the relevant paper-based patient- and caregiver-reported outcome measures to complete either during the visit to the hospital or treatment centre for administration of ERT or at home after leaving the clinic (as described above). Completed questionnaires will be handed back or posted (using a pre-paid envelope) to the hospital or treatment centre staff or, alternatively, responses to the questionnaires completed by patients and caregivers after leaving the clinic (bespoke questionnaire, second and third bespoke fatigue Likert scale and first WPAI questionnaire) may be collected over the telephone during a call with a member of the patient's care team. The hospital or treatment centre staff will forward the completed questionnaires to the study management company for entry into a bespoke study database in Microsoft Excel™. Entry to the study database will be restricted (by password protection) to only those members of staff directly involved with the study.

Data will be prepared for analysis using R statistical software version 3.4.1, Stata™ (StataCorp LLC) version 14 and/or Microsoft Excel™. Data management and handling of data will be conducted according to the study-specific data management plan (DMP).

9.9.2 Data analysis

A detailed description of study analysis and reporting will be provided in a separate statistical analysis plan (SAP) to be finalised before data collection is completed. Analyses will be carried out by Open Health using R statistical software, Stata™ (StataCorp LLC) version 14 and Microsoft Excel™. Data will be analysed separately for each participating country and by ERT treatment (agalsidase alfa /agalsidase beta).

The planned statistical analyses are summarised below.

This study is designed to be descriptive in nature; there is no *a priori* hypothesis to be tested and therefore no comparisons between patient subgroups or treatments will be made. Distributions and descriptive statistics of central tendency (medians and arithmetic or geometric means) and dispersion (standard deviation [SD], interquartile range [IQR], range) will be presented for quantitative variables. Categorical variables will be described with frequencies and percentages; where appropriate, distributions, modes, medians, IQR and range will be reported. Where appropriate, 95% confidence intervals (95% CI) will also be presented for means and estimates of proportions. Ordinal variables will be evaluated using either frequencies and percentages or medians and IQR or both depending on the number of possible values for the variable.

Analysis for validated instruments will adhere to the licensed scoring manual. Item and domain scores (if relevant) will be presented.

All percentages will be reported to the nearest whole number; therefore, in reporting study results in tables, figures and associated text, percentages may not add up to 100% due to rounding. For total group/subgroup sizes of less than 10, percentages will not be reported, except under exceptional circumstances. Consideration will be given during data analysis as to whether reporting any of the planned analyses may identify individuals from combinations of variables occurring in very small groups; to preserve participant anonymity such results may be suppressed in the study report and any materials intended for publication.

9.9.3 Missing data

Where dates are ambiguous because of missing day and/or months, standard imputation will be applied: where day is missing the 15th of the month will be assumed; where both day and month are missing the 1st July will be assumed.

For other missing data, the affected analyses will be conducted using only the results of those patients/episodes with data available and the number included in each analysis will be stated.

The number of patients or caregivers with data missing will be reported for each study variable.

9.9.4 Subgroup and sensitivity analyses

The primary endpoint (and secondary endpoint, if numbers are sufficient) analyses will be conducted overall and repeated with stratification of the sample by country and by type of ERT (agalsidase alfa / agalsidase beta). If numbers are sufficient, analyses may be conducted by severity of FD (mild / moderate / severe [to be determined using the patients' baseline information, as described above]).

No sensitivity analyses are planned.

9.9.5 Interim analyses

No interim analyses are planned.

9.10 Quality control

All staff collecting data for the study (site staff and/or external observers) will be provided with data collection guidelines and will receive training in the requirements of the study protocol and correct data collection. This will ensure consistent completion of the eCRF for demographic information, paper CRF for time and motion data collection, and administration of paper questionnaires to patients and caregivers.

Data collection for the prospective time and motion study will be performed by trained external observers from the study management company or by members of the patients' care team at each site, who will also receive training in the time and motion study procedures. The observers will record start and stop times for each task on paper CRFs. It is recommended that 2 timing devices are used in case of failure of one of the devices. For the purposes of quality control, each data collector will transcribe the first 3 completed CRFs into the eCRF within 1 business day of the data collection and the entered data will be reviewed by project management or data management staff from the study management company. If errors or inconsistencies in the data are noted, additional training will be provided to the observers.

This pilot exercise will also be used to confirm that the database and CRF have been designed appropriately and that the data collection methodology is feasible.

Data collection progress will be monitored by local Clinical Research Associates (CRAs) on an ongoing basis and support will be available throughout the entire study period to observers and site study staff as required.

Patient demographic data and data submitted for the time and motion component of the study will be checked for completeness and accuracy by the Open Health data management team using agreed manual and programmed validation checks, which will be specified in the study DMP. Missing values may occur during collection of observational data (e.g. due to stopwatch failure). The frequency of these missing values will be tabulated as part of the data analysis but no queries will be raised. Other queries related to out-of-range values, inconsistent responses and any other data issues will be raised with each site by the data management team at the study management company, and resolutions documented. Study centres will be required to co-operate with the data management team in the resolution of these queries.

No queries will be raised on patient- or caregiver-reported data.

